| Research question and objectives: | 
The primary objective of this prospective NIS is to investigate the comparative effectiveness of Spiolto® Respimat® in the new reusable inhaler vs any free or fixed-dosed triple therapy (LAMA + LABA + ICS) in reducing dyspnea (as measured via mMRC questionnaire) and symptom burden (as measured via CAT™) in COPD patients who are dyspneic despite LABA/ICS maintenance treatment when switched to either Spiolto® Respimat® or to any triple therapy, both in a real-word setting.
 
This study aims to analyze the comparative effectiveness of Spiolto® Respimat® in the new reusable inhaler vs any triple therapy in reducing dyspnea and symptom burden from each individual patient's score difference between baseline and after approximately 12 weeks of treatment. Two descriptive primary endpoints will be assessed:
 
(1) Difference in mMRC (modified Medical Research Council) score at baseline and after end of observation (ca. 12 weeks of treatment, Visit 2)
 
(2) Difference in CAT™ (COPD assessment test) score at baseline and after end of observation (ca. 12 weeks of treatment, Visit 2)
 
Secondary endpoints to be determined and compared in an exploratory manner include:
 
• Patients' general condition according to the Physician's Global Evaluation (PGE) score at baseline and end of the observation period,• Patient satisfaction with inhaler and therapy at end of observation period according to a seven-point ordinal scale (ranging from very dissatisfied to very satisfied as documented in non-interventional BI studies (BI 1237-0042, 1237-0043, 1237-0044, 1237-0045, 1237-0065, 1237-0072),• proportion of responders with $\Delta_{mMRC} \geq 1$ and proportion of responders with $\Delta_{CAT} \geq 2$. 
Descriptive analyses of handling of the new reusable Respimat® inhaler and user experiences will be performed.
 |

| | |
|---|---|
| | 
Additional groupwise descriptive statistics will be calculated with respect to
 
• exacerbations (overall and stratified by levels of eosinophils (where available)),• hospitalizations due to COPD exacerbations,• adherence,• levels of eosinophils (where available in patient documentation),• improvement in dyspnea and responder rates (overall and according to levels of eosinophils (where available)), and• improvement in lung function (overall and stratified by levels of eosinophils; where available in patient documentation) |
| Country(-ies) of study: | Germany |
| Author: | [REDACTED] |
| Marketing authorisation holder(s): | [REDACTED] |
| Date: | 7 June 2019 |

Page 1 of 65

Proprietary confidential information

© 2019 Boehringer Ingelheim International GmbH or one or more of its affiliated companies. All rights reserved.
This document may not - in full or in part - be passed on, reproduced, published or otherwise used without prior written permission

2. LIST OF ABBREVIATIONS

| | |
|------------------|---|
| ADR | Adverse Drug Reaction |
| AE | Adverse Event |
| AEsi | Adverse Event of special interest |
| AMG | Arzneimittelgesetz (German Drug Act) |
| AUC | Area under the Curve |
| BfArM | Bundesinstitut für Arzneimittel und Medizinprodukte (German CA) |
| BI | Boehringer Ingelheim |
| CAT™ | COPD Assessment Test |
| CI | Confidence Interval |
| CML | Clinical Monitor Local |
| COPD | Chronic Obstructive Pulmonary Disease |
| CRA | Clinical Research Associate |
| CRO | Clinical Research Organisation |
| CTCAE | Common Terminology Criteria for Adverse Events |
| DVP | Data Validation Plan |
| eCRF | Electronic Case Report Form |
| EDC | Electronic Data Capture |
| EU | European Union |
| FDC | Fixed Dose Combination |
| FEV ₁ | Forced expiratory volume in one second |
| GCP | Good Clinical Practice |
| GEP | Good Epidemiological Practice |
| GP | General Practitioner |
| GPP | Good Pharmacoepidemiology Practice |
| GOLD | Global Initiative for Chronic Obstructive Lung Disease |
| ICH | International Conference on Harmonisation |
| ICS | Inhalative Corticosteroids |
| IEC | Independent Ethics Committee |
| IPCRG | International Primary Care Respiratory Group |
| IRB | Institutional Review Board |
| ISF | Investigator Site File |
| LABA | Long-acting beta ₂ adrenoceptor agonist |
| LAMA | Long-acting muscarinic antagonist |
| MACE | Major Adverse Cardiovascular Event |
| MAH | Marketing Authorisation Holder |
| MCID | Minimum Clinically Important Difference |
| MedDRA | Medical Dictionary for Drug Regulatory Activities |
| mMRC | Modified Medical Research Council |
| NCI | National Cancer Institute |
| NIS | Non-Interventional Study |

| | |
|------|---|
| PGE | Physician's Global Evaluation |
| PRO | Patient-reported outcome |
| SABA | Short-acting beta ₂ adrenoceptor agonist |
| SADR | Suspected Adverse Drug Reaction |
| SAE | Serious Adverse Event |
| SAMA | Short-acting muscarinic antagonist |
| SGRQ | St. George's Respiratory Questionnaire |
| SmPC | Summary of Product Characteristics |
| TDI | Transitional dyspnea index |
| VFA | Verband Forschender Arzneimittelhersteller |
| WHO | World Health Organization |

4. ABSTRACT

| | | | |
|---|--|---------------------------------|--|
| Name of company: Boehringer Ingelheim Pharma GmbH & Co. KG | | | |
| Name of finished medicinal product: Spiolto® Respimat® | | | |
| Name of active ingredient: R03AL06 Tiotropium bromide and Olodaterol | | | |
| Protocol date: 27 May 2019 | Study number: 1237-0087 | Version/Revision: 2.0 | Version/Revision date: 7 June 2019 |
| Title of study: | EVELUT® : Assessment of dyspnea and other symptom burden as patient reported outcomes (PRO) in patients with chronic obstructive pulmonary disease (COPD), symptomatic on LABA/ICS maintenance therapy (now) treated with Spiolto® Respimat® (tiotropium/olodaterol) in comparison to open or fixed triple combination treatment (LAMA + LABA + ICS) in routine clinical practice Author: [REDACTED] | | |
| Rationale and background: | 
Dyspnea is the most relevant symptom burden that leads to diagnosis, initiation or change of maintenance COPD therapy. Clinical studies have demonstrated that the LAMA-LABA combination Spiolto® Respimat® significantly improves dyspnea in COPD patients¹. However, real world data with regard to the effects of dual bronchodilation with Spiolto® Respimat® vs triple therapy (LAMA + LABA + ICS) in COPD patients that are dyspneic and symptomatic despite being on a LABA/ICS maintenance therapy are not yet available.
 
This non-interventional study (NIS) aims to investigate alleviation of dyspnea and other symptom burden in COPD patients who are symptomatic (dyspneic) despite LABA/ICS maintenance therapy and who are switched to Spiolto® Respimat® in the new reusable inhaler or triple therapy at the discretion of their attending physician. If a patient has symptoms other than dyspnea that led to a change from LABA/ICS, these patients will also be included into the study; except for those classified as acute exacerbations by the treating physician. Dyspnea will be assessed with the mMRC questionnaire; symptom burden will be evaluated by the CAT™ questionnaire.
 | | |

| Name of company: Boehringer Ingelheim Pharma GmbH & Co. KG | | | |
|--|---------------|-------------------|------------------------|
| Name of finished medicinal product: Spiolto® Respimat® | | | |
| Name of active ingredient: R03AL06 Tiotropium bromide and Olodaterol | | | |
| Protocol date: | Study number: | Version/Revision: | Version/Revision date: |
| 27 May 2019 | 1237-0087 | 2.0 | 7 June 2019 |
| 
The mMRC and CAT™ are widely used simple measures of breathlessness and symptoms and are easy to complete; they relate well to other measures of health status and can therefore be used to monitor dyspnea and symptoms in COPD patients². Furthermore, the questionnaires are responsive to intervention, predict future mortality risk, and, finally, have been translated and validated in Germany^{3, 4, 5, 6}.
 
Treatment guidelines recommend effective bronchodilation as the basis of COPD therapy in most patients. In contrast, ICS is seen as an obligatory part of pharmacological treatments only in patients with concomitant asthma or as a therapeutic option for patients that further exacerbate despite dual bronchodilation therapy or that have a high risk for exacerbation and high levels of eosinophils^{7, 8, 9}.
 
However, LABA/ICS-fixed dose combinations (FDC) remain the most widely prescribed therapy in COPD. Dyspnea is one of the most relevant patient-reported symptoms in COPD. In order to achieve better symptom control, therapy can be adjusted by the attending physician from LABA/ICS to either dual bronchodilation or any triple therapy (free or fixed-dose: dual bronchodilation plus inhaled corticosteroid, ICS).
 
BI developed a novel reusable Respimat® inhaler to simplify assembly and daily use, optimize the dose indicator and make it reusable with up to 6 cartridges. The updated design is intended to improve the usability and environmental impact of the Respimat® inhaler, while preserving the pharmaceutical features and basic functions of the disposable Respimat® inhaler.
 
According to GOLD 2019, it is a clinical core question whether inhalative COPD therapy of patients, who suffer from dyspnea and other symptoms despite LABA/ICS treatment, should be switched to either LAMA/LABA or triple therapy (LAMA + LABA + ICS; free or fixed-dose).
 | | | |

| | | | |
|---|--|---------------------------------|--|
| Name of company: Boehringer Ingelheim Pharma GmbH & Co. KG | | | |
| Name of finished medicinal product: Spiolto® Respimat® | | | |
| Name of active ingredient: R03AL06 Tiotropium bromide and Olodaterol | | | |
| Protocol date: 27 May 2019 | Study number: 1237-0087 | Version/Revision: 2.0 | Version/Revision date: 7 June 2019 |
| | | | 
The recent GOLD update supports the design of this study. GOLD 2019 suggests that patients who do not suffer from frequent exacerbations and who present with persistent breathlessness or exercise limitation on LABA/ICS treatment, should either be escalated to triple therapy or switched to LAMA/LABA. A switch from LABA/ICS to LAMA/LABA is suggested in case the initial indication of ICS was inappropriate or if there has been a lack of response to ICS treatment, or if ICS side effects warrant discontinuation.
 
Currently, no prospective clinical evidence is available that supports a direct switch from LABA/ICS to LAMA/LABA instead of moving to triple therapy if an initial indication for ICS use is lacking. Therefore, this study aims to investigate if patients who are symptomatic under LABA/ICS treatment and are switched to LAMA/LABA do not suffer more from dyspnea and symptoms compared to triple therapy.
 |
| Research question and objectives: | 
The primary objective of this NIS is to investigate the changes in dyspnea (as measured via mMRC (Modified Medical Research Council) questionnaire) and symptom burden (as measured via CAT™ (COPD Assessment Test)) in COPD patients who are dyspneic despite LABA/ICS maintenance treatment when switched to either Spiolto® Respimat® in the new reusable inhaler or to any triple therapy (free or fixed-dosed).
 
More precisely, this study aims to assess analyze the comparative effectiveness of Spiolto® Respimat® in the new reusable inhaler vs any triple therapy in changes in dyspnea and symptom burden from each individual patient's difference between baseline and after approximately 12 weeks of treatment.
 
Two primary endpoints will be assessed:
 
• Difference in mMRC (modified Medical Research Council) score at baseline and after end of observation (approx. 12 weeks of treatment, Visit 2)• Difference in CAT™ (COPD assessment test) score at baseline and after end of observation (approx.. 12 weeks of treatment, Visit 2) | | |

| | | | |
|---|--|---------------------------------|--|
| Name of company: Boehringer Ingelheim Pharma GmbH & Co. KG | | | |
| Name of finished medicinal product: Spiolto® Respimat® | | | |
| Name of active ingredient: R03AL06 Tiotropium bromide and Olodaterol | | | |
| Protocol date: 27 May 2019 | Study number: 1237-0087 | Version/Revision: 2.0 | Version/Revision date: 7 June 2019 |
| 
MMRC and CAT™ are both of interest as primary endpoints. The comparative effectiveness on the primary endpoints will be determined based on model coefficients (along with 95% confidence intervals) and statistical testing of these coefficients. Since the study is exploratory in nature, no multiplicity adjustment is planned.
 
Secondary endpoints to be determined and compared in an exploratory manner include
 
• patients' general condition according to the Physician's Global Evaluation (PGE) score at baseline and end of the observation period of approximately 12 weeks,• patient satisfaction with inhaler and therapy at end of observation period according to a seven-point ordinal scale (ranging from very dissatisfied to very satisfied as documented in non-interventional trial (BI 1237-0042, 1237-0043, 1237-0044, 1237-0045, 1237-0065, 1237-0072),• proportion of responders with $\Delta_{mMRC} \geq 1$ and proportion of responders with $\Delta_{CAT} \geq 2$ | | | |
| Study design: | 
Open-label comparative multicentric cohort study according to §4, section 23 and §67, section 6 German Medicines Act.
 
All included COPD patients receive a LABA/ICS maintenance treatment until visit 1 and are switched at visit 1 at the discretion of the attending physician to either tiotropium/olodaterol in the new reusable Respimat® inhaler or any triple therapy (LAMA + LABA + ICS) according to clinical routine. Observational period will be approximately 12 weeks after switch, which is the average time between two medical consultations.
 
NIS based on newly collected data.
 | | |
| Population: | 
COPD patients on LABA/ICS maintenance therapy with dyspnea ($mMRC \geq 1$) and other symptoms ($CAT^{\text{TM}} \geq 10$), who are switched to either Spiolto® Respimat® in the new reusable inhaler or any triple therapy (LAMA + LABA + ICS) as an open or fixed combination according to approved SmPCs at baseline at the discretion of their attending physician.
 | | |

| | | | |
|--|-----------------------------------|---------------------------------|--|
| Name of company: Boehringer Ingelheim Pharma GmbH & Co. KG | | | |
| Name of finished medicinal product: Spiolto® Respimat® | | | |
| Name of active ingredient: R03AL06 Tiotropium bromide and Olodaterol | | | |
| Protocol date: 27 May 2019 | Study number: 1237-0087 | Version/Revision: 2.0 | Version/Revision date: 7 June 2019 |
| 
Inclusion Criteria:
 
• Diagnosis of COPD• Symptomatic (with regard to dyspnea (mMRC Dyspnea score ≥ 1) AND with regard to symptoms (CAT™ Score ≥ 10) at the same time)• Patients on LABA/ICS maintenance therapy who are switched to Spiolto® Respimat® in the new reusable inhaler or a free/fixed triple combination of LAMA + LABA + ICS at Visit 1 at the discretion of the treating physician.• Adults who are contractually capable and mentally able to understand and follow the instructions of the study personnel• Male or female• Patients aged ≥ 40 years of age• Written informed consent prior to study participation• The patient is willing and able to follow the procedures outlined in the protocol | | | |
| 
Exclusion Criteria:
 
• Patients with contraindications acc. to SmPC• Patients not on LABA/ICS maintenance treatment at visit 1, eg, mono or dual bronchodilation only, ICS only, or a triple combination of LAMA + LABA + ICS (either as a fixed combination product or as separate components)• Lack of informed consent• Pregnant and/or lactating females• Acute exacerbation of COPD (within 4 weeks prior to Visit 1) | | | |

| | | | |
|---|--|---------------------------------|--|
| Name of company: Boehringer Ingelheim Pharma GmbH & Co. KG | | | |
| Name of finished medicinal product: Spiolto® Respimat® | | | |
| Name of active ingredient: R03AL06 Tiotropium bromide and Olodaterol | | | |
| Protocol date: 27 May 2019 | Study number: 1237-0087 | Version/Revision: 2.0 | Version/Revision date: 7 June 2019 |
| 
• Frequently exacerbating patients, i. e. patients with ≥ 2 moderate exacerbations within the last 12 months or ≥ 1 exacerbation leading to hospitalization within the last 12 months• Acute respiratory failure (pH $<7,35$ and / or respiratory rate $>30/\text{min}$ within 3 months prior to Visit 1)• History or current diagnosis of asthma• History or current diagnosis of asthma-COPD overlap• History or current diagnosis of allergic rhinitis within the last 5 years• History or current diagnosis of lung cancer within the last 5 years• Participation in a parallel interventional clinical trial | | | |
| Variables: | 
The following parameters will be collected and assessed at visit 1 and/ or visit 2:
 
• Specialization of attending physician (GP, pulmonologist, internal specialist)• Patient demographics (age, gender, height, weight)• History of COPD• Rationale for changing COPD maintenance therapy• Reported number and severity of exacerbations in the last 12 months• Number of exacerbations leading to hospitalization in the last 12 months according to medical files• Device training yes/no, reason for no training• GOLD patient groups (A, B, C, D, calculatedⁱ) based on GOLD guidelines 2019 | | |

ⁱ GOLD patient group (A, B, C or D) will be automatically calculated within the eCRF based on available exacerbation history, mMRC and CAT

| | | | |
|---|-----------------------------------|---------------------------------|--|
| Name of company: Boehringer Ingelheim Pharma GmbH & Co. KG | | | |
| Name of finished medicinal product: Spiolto® Respimat® | | | |
| Name of active ingredient: R03AL06 Tiotropium bromide and Olodaterol | | | |
| Protocol date: 27 May 2019 | Study number: 1237-0087 | Version/Revision: 2.0 | Version/Revision date: 7 June 2019 |
| 
• GOLD spirometric classifications (1, 2, 3, 4 and date of exam, where availableⁱⁱ)• Eosinophils in peripheral blood and date of exam, where available• Smoking history, current status (current smokers, former smokers, and never smokers) and pack-years• Concomitant diseases / comorbidities such as cardiovascular disease, diabetes mellitus, musculoskeletal impairment, renal diseases, liver diseases, osteoporosis, gastroesophageal reflux (GERD)• Current (within the last 6 months) COPD related and other relevant concomitant medication such as beta-blockers, beta-agonists, corticosteroids, or proton pump inhibitors at date of Visit 1• Assessment of the severity of dyspnea based on the Modified Medical Research Council Questionnaire (mMRC), completed by the patient• Health and functional status by CAT™ questionnaire, completed by the patient• General condition of patient based on Physician's Global Evaluation (PGE) at the beginning and at the end of the study• Patient satisfaction with inhaler, inhalation, treatment and handling, according to a seven-point ordinal scale (ranging from very dissatisfied to very satisfied)• Safety: ADRs (serious and non-serious), fatal AEs, pregnancies during the study• Patient's willingness to continue or discontinue treatment with either triple therapy or Spiolto® Respimat® after the study (yes/no)• Rationale for treatment discontinuation (if applicable) | | | |

ⁱⁱ GOLD stage 1-4 spirometric classification of airflow limitation based on post-bronchodilator FEV1

| | | | |
|---|---|---------------------------------|--|
| Name of company: Boehringer Ingelheim Pharma GmbH & Co. KG | | | |
| Name of finished medicinal product: Spiolto® Respimat® | | | |
| Name of active ingredient: R03AL06 Tiotropium bromide and Olodaterol | | | |
| Protocol date: 27 May 2019 | Study number: 1237-0087 | Version/Revision: 2.0 | Version/Revision date: 7 June 2019 |
| Data Sources: | 
To be completed by the physician:
 
• Patient demographics• Patient medical files• Physician's Global Evaluation (PGE) at visit 1 and visit 2• Patient satisfaction with inhaler, inhalation, treatment and handling• Patient's willingness to continue or discontinue treatment 
To be completed by the patient at visit 1 and at visit 2:
 
• Health and functional status by CAT™ questionnaire• mMRC breathlessness scale | | |
| Study size: | Ca. 900 patients, approx. 150 recruiting sites | | |
| Data analysis: | 
Main analysis:
 
The estimation of the relative treatment effect concerning the primary outcomes is subject to potential confounding; therefore adjusted analyses are required and will be performed. Multiple analytical approaches will be applied to allow an assessment of the sensitivity of the results to these approaches:
 
• Propensity score matching (primary analysis; requires data to be discarded from the analysis)• Propensity score weighting (uses the complete data set)• Multivariable regression modeling (uses the complete data set) 
The relative treatment effect will be determined based on model coefficients (along with 95% confidence intervals) and statistical testing of these coefficients. Since the study is exploratory, no multiplicity adjustment is planned.
 | | |

| | | | |
|--|--|---------------------------------|--|
| Name of company: Boehringer Ingelheim Pharma GmbH & Co. KG | | | |
| Name of finished medicinal product: Spiolto® Respimat® | | | |
| Name of active ingredient: R03AL06 Tiotropium bromide and Olodaterol | | | |
| Protocol date: 27 May 2019 | Study number: 1237-0087 | Version/Revision: 2.0 | Version/Revision date: 7 June 2019 |
| Handling of missing data: Multiple imputation will be applied to estimate the propensity score model and the multivariable regression models. In descriptive analyses, the fraction of missing observations will be reported. | | | |
| Safety: | Adverse drug reactions (ADRs; serious and non-serious), fatal adverse events (AEs), pregnancies during the study | | |
| Milestones: | Start of data collection | Q2 2019 | |
| | End of data collection | Q2 2020 | |
| | Final report of study results | Q4 2020 | |

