9.4.2 Symptomatic Burden: mMRC and CATTM

The modified Medical Research Council (mMRC) scale is a 5-point (0–4) scale based on the severity of dyspnoea. The mMRC will be used to assess the breathlessness state of the patient with just one question: "When do you experience dyspnoea?", covering five everyday activities, potentially leading to dyspnoea and giving an according rate of 0 to 4 points. The MCID is a change of 1.0 point. It will be applied before the treatment and after approximately 12 weeks of treatment

The COPD Assessment Test (CATTM) was developed as a simple instrument to assess health status in patients with COPD¹². The CATTM consists of eight items, each formatted as a semantic six-point differential scale, making the tool easy to administer and easy for patients to complete³⁵. These eight items cover cough, phlegm, chest tightness, breathlessness when going up hills/stairs, activity limitations at home, confidence leaving home, sleep and energy. Each item is scored from 0 to 5 giving a total score range from 0 to 40, corresponding to the best and worst health status in patients with COPD, respectively³⁴. The MCID is a change of 2.0 points³⁶.

The questionnaire will be filled out by the patient and entered into the database. Patients will be asked to complete the CATTM in order to evaluate their health and functional status before treatment with Spiolto[®] Respimat[®] or triple therapy, respectively, and after approximately 12 weeks.

Additionally, the mMRC stage and CATTM scores collected from the patient as well as the exacerbation history will be used to automatically calculate the GOLD patient group (A, B, C, or D) in the eCRF.

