9.4.3 Patient Satisfaction

The 7-item satisfaction scale with divisions from very dissatisfied to very satisfied to be completed at Visit 1 and Visit 2 to measure patient satisfaction with inhaler use, is a Likert-scale without validation status for the intended use. However, the application of Likert-Scales has been well established in a range of comparable situations^{37, 38, 39}.

Patient's willingness to continue treatment is assessed by a yes/no question plus reasons for non-willingness.

9.5

STUDY SIZE

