6.7 BASELINE, TIME WINDOWS AND CALCULATED VISITS

Baseline visit (Visit 1) will include historical and demographic data as well as registration and initial examination.

Treatment with Spiolto® Respimat® will be documented at visit 1 and visit 2, after approximately 12 weeks of treatment.

Proprietary confidential information © 2020 Boehringer Ingelheim International GmbH or one or more of its affiliated companies

The mMRC breathlessness scale as well as the CAT™ questionnaire (health and functional status) is completed by the patient at visit 1 and (after approximately 12 weeks of treatment) visit 2.

In addition, the PGE is completed by the physician at visit 1 and visit 2 as well as satisfaction survey at visit 1 (regarding the preceding therapy) and visit 2 (regarding the new therapy).

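### The plan assigns the patient satisfaction scale to the prescribing physician and nowhere to the patient, which leaves a compared secondary endpoint open to the prescriber's influence

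*Protocol*

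**What the plan says.** The Data Sources entry of the protocol abstract (section 4) has two lists.

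- The first is headed "To be completed by the physician". It holds demographics, medical files, the Physician's Global Evaluation (PGE), "Patient satisfaction with inhaler, inhalation, treatment and handling", and the patient's willingness to continue.
- The second is headed "To be completed by the patient at visit 1 and at visit 2". It holds only CAT and mMRC.

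Other places that bear on the respondent:

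- **Protocol 9.4.3** describes "The 7-item satisfaction scale with divisions from very dissatisfied to very satisfied to be completed at Visit 1 and Visit 2" and does not say by whom.
- **SAP 6.7** first states that the patient completes mMRC and CAT at both visits. It then says that "the PGE is completed by the physician at visit 1 and visit 2 as well as satisfaction survey at visit 1" (about the preceding therapy) and at visit 2 (about the new one).
- **Protocol 9.4.2**, on CAT, separates answering from data entry: "The questionnaire will be filled out by the patient and entered into the database".

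Satisfaction is a secondary endpoint (Protocol 9.3.2.2, SAP 5.2). SAP 5.2 and 7.4 plan a between-group comparison of the secondary endpoints by propensity score matching.

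**The concern.** Satisfaction is the patient's own view. Under the plan as written, the form goes to someone who knows the treatment and chose it (Protocol 9.1, 9.2.3, 9.9). Two routes of influence are possible. If the physician rates satisfaction, the endpoint measures the physician's impression. If the physician asks and writes down the reply, the patient answers in front of the prescriber and the prescriber does the recording.

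Matching cannot remove either effect, because both arise after treatment is chosen. The propensity model carries only the physician's specialty (SAP 7.3), and centre is not in the statistical model (SAP 6.5). Protocol 9.2.3 encourages a 1:1 split within each site, so one physician may well report on patients in both groups. A preference between the treatments would then act directly on the contrast.

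At stake is whether a between-group result labelled as patient satisfaction can be attributed to patients.

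**Working it through.** **Step 1: who completes what, place by place.**

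| Place | CAT and mMRC | PGE | Satisfaction |
|---|---|---|---|
| Protocol 4, Data Sources | patient | physician | physician |
| Protocol 4, Variables; 9.3 | marked as patient-completed | physician's evaluation | no respondent named |
| Protocol Table 9.2.3.1 | marked as patient-completed | physician's evaluation | no respondent named |
| Protocol 9.4 | CAT: patient, stated (9.4.2) | treating physician, stated (9.4.1) | no respondent named (9.4.3) |
| SAP 6.7 | patient | physician | same clause as the physician-completed PGE |
| Protocol Annex 1 | forms listed | form listed | no form listed |

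One place assigns satisfaction to the physician outright, one most naturally reads that way, the rest are silent, and none assigns it to the patient. No listed form settles the question.

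**Step 2: could the physician heading mean data entry only?** Against this, CAT is filled out by the patient and then entered, yet it stands in the patient list, so the two lists do not simply sort items by who types them in. For it, the physician list also holds demographics and medical files, which are recorded and not rated, and willingness to continue, which 9.4.3 describes as a yes/no question with reasons. The list mixes rated, transcribed and asked items. The text does not decide between the physician rating satisfaction and the physician recording the patient's answer.

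**Step 3: is there a figure to reproduce?** None for satisfaction: no standard deviation, expected difference or rater effect is given. The sample size (Protocol 9.5.1) does not depend on who completes the scale. It is used below only for the number of evaluable patients: 432 per group less 40% is 432 × 0.6 = 259.2, which agrees with the stated 259.

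**Step 4: illustration of sensitivity.** Assumptions, not from the documents: 259 per group, no true difference, a normal approximation with independent groups, a two-sided 5% test, and a differential rating shift of d standard deviations between groups.

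- Standard error in SD units: √(2/259) = 0.0879.
- False-positive rate: 1 − Φ(1.96 − d/0.0879) + Φ(−1.96 − d/0.0879).

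| d (SD) | False-positive rate |
|---|---|
| 0 | 5.0% |
| 0.05 | 8.8% |
| 0.1 | 20.7% |
| 0.2 | 62.4% |
| 0.3 | 92.7% |

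The row d = 0 matters as much as the others: if physicians favour their own choice equally in both groups, the contrast does not move. The table shows only that a small differential shift would not be harmless at this sample size. It does not show that such a shift exists.

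**The case against.** The case for leaving this as a minor query has several sound parts.

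- **The mechanism has no known direction.** The physician chooses the treatment in both groups. Recording in line with one's own choice could raise both groups alike. A reader might infer that the comparison is biased, perhaps towards the sponsor's product. The documents do not support that.
- **Transcription is possible.** A reader might also infer that the physician rates satisfaction in the patient's place. The mixed content of the physician list and the loose construction of SAP 6.7 do not establish this.
- **The study title does not help.** It calls dyspnea and symptom burden patient-reported outcomes; it does not mention satisfaction.
- **Satisfaction is not the main evidence on the new inhaler.** The primary endpoints are mMRC and CAT, and Protocol 8.1 plans separate descriptive analyses of handling and user experience. Satisfaction is exploratory, on a scale that 9.4.3 itself describes as not validated for this use.
- **Self-completion is not a full remedy.** Patients know their treatment too.

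All of this stands and limits the point to a risk of unknown size and direction. It does not remove the point. If transcription was intended, no passage says so, and asking and recording still puts the prescriber between the patient and the answer.

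**Conclusion.** The point holds as a risk of bias, not as a shown bias. The plan gives the satisfaction scale to an unblinded prescriber in the abstract, most naturally does so again in SAP 6.7, and assigns it to the patient nowhere. The endpoint is then compared between groups, and the adjustment cannot reach an effect of the person completing the form.

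Size and direction cannot be computed from the documents; the false-positive rates above rest wholly on the stated assumptions. The consequence is confined to satisfaction and, on the same reasoning, to willingness to continue. The mMRC and CAT results and the sample size are not touched. The correction is worth making because it is cheap and settles the matter whichever reading was intended.

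**What to change.** - In the abstract's Data Sources, move patient satisfaction to the list headed "To be completed by the patient at visit 1 and at visit 2".
- Mark it as patient-completed in Table 9.2.3.1, Protocol 9.3 and Protocol 9.4.3, as is done for mMRC and CAT in the table and in 9.3.
- Reword SAP 6.7 so that the physician completes the PGE and the patient completes the satisfaction survey.
- State the respondent for willingness to continue, since that is also the patient's view.

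Protocol section 6 planned the end of data collection for Q2 2020, and the last entry in the SAP history table is dated 17 July 2020, so the data may already be in. In that case, state in the SAP and the report who answered and how, and interpret the between-group comparison accordingly.

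The cost is wording changes and one more short patient form at each of two existing visits. The change removes the prescriber's part in the answer; it does not remove the effect of patients knowing their treatment.
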